Hypothesis: Remote perioperative telemonitoring reduces postoperative complications in the 30 days after major abdominal cancer surgery.

Aim 3: Compare early withdrawal (dropout or loss of accelerometer device) between the comparators.

Hypothesis: Remote perioperative telemonitoring does not excessively burden patients and families.

Aim 4: Explore perioperative telemonitoring care-related experiences (acceptability, technology usability, uptake/integration) among patients, families, and surgeons/nurses through qualitative focus groups and open-ended exit surveys.

Research Question: What are the various stakeholder's perspectives on remote perioperative telemonitoring care?

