The Aim's primary endpoint will be the percent change from preoperative baseline in daily step count during the first 2 weeks post-discharge from hospital (measured on Discharge Day, Day +7, and Day +14). percent change from preoperative baseline in daily step count during the first 2 weeks post-discharge from hospital (measured on Discharge Day, Day +7, and Day +14). To recognize that these data may be missing not at random (ie, due to adverse event, distress, or withdrawal of consent), the effect of study intervention on primary endpoint will be modeled jointly with early withdrawal from data collection of that endpoint. Within the joint model, the sub-model for the primary endpoint will use generalized linear mixed modeling (with treatment and covariates as fixed factors, patient ID as random factor), while the other sub-model will analyze time to early withdrawal (Aim 3's primary endpoint) using proportional hazards regression. Similar joint modeling will be carried out for Aim 1's secondary endpoints (change from baseline in sedentary time, general symptoms, disease-specific symptoms).

Aim 2 – Because the CCI is derived from data routinely entered in the medical chart, no loss to follow-up is anticipated for this endpoint. A sample size of 332 subjects randomized 1:1 will provide (per East 6.5 software) 88% power to detect the hypothesized CCI benefit, using a 1-sided test of proportions, unpooled estimate of variance, critical p-value for efficacy=0.024, cumulative alpha=0.025.

The Aim's primary endpoint will be maximum Comprehensive Complications Index (CCI) during the 30 days post-discharge. Maximum CCI will be categorized as above vs below 15, and logistic regression will be used to evaluate the effect of study intervention. The Aim's secondary endpoint, time to hospital readmission through 90 days, will be subjected to survival analysis, handling any early withdrawal from study as a competing endpoint.

Aim 3 - The trial's sample size of n=332 will provide (per SAS software, PROC POWER for two-sample comparison of proportions) at least 80% power.

Treatment will be evaluated for association with this Aim's primary endpoint, time to early withdrawal, using proportional hazards regression. This analysis will be generated as a sub-model of the joint modeling for Aim 1.

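### Aim 3 hypothesises that telemonitoring is not excessively burdensome, but tests early withdrawal only for association, with no margin or confidence-interval criterion, and its power statement cannot be checked

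*Combined protocol and SAP*

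**What the plan says.** Section 1.0 states the Aim 3 hypothesis: "Remote perioperative telemonitoring does not excessively burden patients and families". The comparison under that aim is: "Compare early withdrawal (dropout or loss of accelerometer device) between the comparators".

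Section 13.2 gives the analysis: "Treatment will be evaluated for association with" time to early withdrawal, the primary endpoint of the aim, by proportional hazards regression. It adds that this is a sub-model of the Aim 1 joint model. The synopsis says the same.

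The Aim 3 sample size statement in section 13.2 is one sentence: "The trial's sample size of n=332 will provide (per SAS software, PROC POWER for two-sample comparison of proportions) at least 80% power". It names no withdrawal rates, difference, hazard ratio, margin, alpha or sidedness. Aim 1, in the same section, does state its effect size, alpha and sidedness.

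No section says how large an excess in withdrawal would count as excessive, or what result would lead to the conclusion that it is not.

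**The concern.** The hypothesis claims that an excess is absent or small enough to accept. The planned analysis asks whether the arms differ. These are different questions. A test of association can support the hypothesis in only one way, by showing significantly less withdrawal with telemonitoring, and that is more than the hypothesis claims. In every other case the test either rejects in the wrong direction or fails to reject. Failure to reject says nothing about how large an excess remains compatible with the data, and it becomes more likely as events become fewer or data noisier.

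Burden is the subject of one of the trial's three quantitative aims and bears on whether telemonitoring would be adopted. With no criterion fixed in advance, what counts as not excessive would be settled after the data are seen.

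**Working it through.** **The plan's own figure.** The claim of "at least 80% power" cannot be reproduced because none of the inputs needed is given. It can only be inverted, to ask what excess would be detected with 80% power.

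**Inputs.**
- Patients per arm: 166 (n=332 in section 13.2, allocated 1:1). Section 3.1 describes 332 as those with complete evaluable data after attrition, out of 398 (199 per arm), so 199 is shown as well.
- Alpha: one-sided 0.025, borrowed from Aim 1 because Aim 3 gives none.
- Control withdrawal: assumed, 5% to 30%. The nearest figure in the plan is 20% accelerometer attrition by Day 14 over both arms (Aim 1). That is neither a control-arm rate nor withdrawal over the whole study, which is what Aim 3 counts.

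**Comparison of proportions (the method that the plan names).** With unpooled variance, power = Φ(d/SE − 1.96), where SE = √{[p(1−p) + (p+d)(1−p−d)]/n}. For p = 0.20, d = 0.10 and n = 166, SE = √[(0.16 + 0.21)/166] = 0.0472. Then 0.10/0.0472 − 1.96 = 0.158, so power is 56%.

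| Assumed control rate | Power for a 10-point excess, 166 per arm | Same, 199 per arm | Excess needed for 80% power, 166 per arm |
|---|---|---|---|
| 5% | 87% | 92% | 8.9 points |
| 10% | 73% | 81% | 11.0 points |
| 20% | 56% | 64% | 13.5 points |
| 30% | 48% | 56% | 14.7 points |

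With pooled variance the figures move by less than one point of power and by about 0.1 point of excess.

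**Proportional hazards (the planned test).** Events are assumed to be 20% of 332, about 66. With 1:1 allocation, SE(log HR) ≈ 2/√66 = 0.246.
- Hazard ratio with 80% power: exp[(1.96 + 0.842) × 0.246] ≈ 1.99.
- Power at a hazard ratio of 1.5: Φ(0.405/0.246 − 1.96) ≈ 38%.
- Largest observed hazard ratio that is not significant at two-sided 0.05: exp(1.96 × 0.246) ≈ 1.62. Its upper 95% limit is then 1.62² ≈ 2.6.

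With 80 events (20% of 398), 80% power needs a hazard ratio of about 1.87, and an observed 1.55 would be just non-significant, with an upper limit of about 2.4. Withdrawal over the whole study could give more events than either assumption.

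**What a margin-based conclusion could exclude.** With equal true rates p, the smallest margin excluded with 80% power is (1.96 + 0.842) × √[2p(1−p)/n]. At p = 0.20 this is 12.3 points at 166 per arm and 11.2 points at 199. At p = 0.10 and 166 per arm it is 9.2 points. Conversely, at p = 0.20 a 10-point margin needs 252 per arm and a 5-point margin needs 1005 per arm.

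**The case against.** A reader might infer two stronger things, and the documents support neither.

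The first is that the plan will treat a non-significant result as proof of no excess. No section says so. Aim 3 has no decision rule at all, so the defect is a missing rule and not a wrong one. The probability of missing a true excess is therefore not the probability of a false conclusion under the plan.

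The second is that Aim 3 is underpowered. The 80% figure is uncheckable, which is not the same as false. For a 10-point excess, power is 87% if control withdrawal is 5% and 48% if it is 30%. Whether either is too low depends on a margin that the plan never sets.

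It can also be said that proportional hazards regression yields a confidence interval as a matter of course, and that a narrow one would be informative. That is true, but the plan neither commits to basing the conclusion on the interval nor gives a limit to judge it against.

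Finally, section 13.2 says that exit-survey and focus-group data will help to interpret Aims 1 to 3, including burden. Those data add context. However, the survey paired with early withdrawal is given to the telemonitoring arm only, at Day 90, so it has no comparator and is not timed to withdrawal. It does not replace a criterion.

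Aim 3 does not affect the tests of the trial's primary endpoints, steps and complications. That limits the weight of the point but does not remove it.

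**Conclusion.** The concern holds in this form: the stated analysis cannot establish the stated Aim 3 hypothesis unless withdrawal is significantly lower with telemonitoring, and the power statement lacks its inputs and refers to a test other than the planned one. Both follow from the text of sections 1.0 and 13.2 without any assumption.

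The size is illustrative. At one-sided 0.025 and 166 per arm, 80% power needs an excess of roughly 9 to 15 points over assumed control rates of 5% to 30%, or a hazard ratio near 2.0 with an assumed 66 events. A non-significant result could therefore leave a hazard ratio of about 2.6 within the 95% interval. More events would narrow this. They would not turn a test of association into evidence of no excess. The point should be corrected, but it does not threaten the primary analyses.

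**What to change.** In the Aim 3 part of section 13.2:

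1. Report the hazard ratio for early withdrawal and the difference in cumulative withdrawal, each with a 95% confidence interval.
2. Conclude that burden is not excessive only if the upper limit lies below a margin fixed before the data are seen, on a named scale. The sponsor should justify the margin by what patients and clinicians would accept, and not derive it from the sample size.
3. State that a non-significant test alone does not support the hypothesis.
4. If no margin can be justified, report the estimate and interval and make no claim of no excess.
5. Restate power for the planned analysis, giving assumed withdrawal, event count, alpha, sidedness and margin. Base it on the intention-to-treat set, which section 13.2 limits to randomised patients who undergo the planned surgery, so it has at most 398 patients.

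The cost is plan wording and a sponsor decision on the margin. No new data are needed. The real limitation is that a tight margin may not be excludable at this size: at 20% withdrawal in both arms, 80% power is available only for a margin of about 12 points at 166 per arm, or 11 at 199. If the justified margin is smaller, option 4, or stating openly that power for the margin is lower, is the honest course.

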5.2 Planned Duration of Therapy

Study participation is planned for approximately 3-4 months. The timeframe covers before surgery, postop acute care, and 90 days post-discharge.

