10.0 Study Calendar

Table 4. Outcome Measures by Aims and Assessment Time Points

	Measures	Before Surgery (T1)	Pre-Discharge (T2)	Day 7 (T3)	Day 14 (T4)	Day 30 (T5)	Day 60 (T6)	Day 90 (T7)
Preop Functional Assessment	6 Minute Walking Time (6MWT)	X						
	Timed Up and Go (TUG)	X						
	Short Physical Performance Battery (SPPB)	X						
Aim 1	Functional Recovery (steps taken, sedentary time)	X	X	X	X	X	X	X
	General Symptoms - MD Anderson Symptom Inventory (MDASI)	X	X	X	X	X	X	X
Aim 2	Post-Operative Complications – CCI		X	X	X	X	X	X
	Hospital Readmissions			X	X	X	X	X
Aim 3	Early withdrawal (dropout, loss of device)							Throughout the Study
Aim 4	Open-Ended Patient Exit Survey							X
	Patients/Families/Surgeon/Nurses Experience – Focus Groups							Year 2-3, Month 22-30

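### Aim 3's only withdrawal analysis is a sub-model of the two-week Aim 1 joint model, with its horizon and link unstated, although early withdrawal is defined over the whole study

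*Combined protocol and SAP*

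**What the plan says.** Section 1.0 states Aim 3 as "Compare early withdrawal (dropout or loss of accelerometer device) between the comparators", under the hypothesis "Remote perioperative telemonitoring does not excessively burden patients and families". Neither carries a time window. Table 4 in section 10.0 supplies one: withdrawal is recorded "Throughout the Study". Section 5.2 says of participation: "The timeframe covers before surgery, postop acute care, and 90 days post-discharge".

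Section 13.2 evaluates treatment against "time to early withdrawal, using proportional hazards regression", and continues: "This analysis will be generated as a sub-model of the joint modeling for Aim 1". The synopsis says the same.

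The Aim 1 text in section 13.2 describes that joint model. Its longitudinal outcome is the percent change in daily steps "during the first 2 weeks post-discharge from hospital (measured on Discharge Day, Day +7, and Day +14". The treatment effect on that outcome is "modeled jointly with early withdrawal from data collection of that endpoint". The longitudinal part is a generalized linear mixed model with a random patient effect, and the other part is a proportional hazards regression of time to early withdrawal.

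Three things are not stated: a censoring day for the hazard part, how the two parts are linked, and which Aim 1 joint model (primary or a secondary endpoint) supplies the Aim 3 result. No separate Cox, Kaplan-Meier or cumulative-incidence comparison of withdrawal is described.

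**The concern.** A patient who leaves on Day 40 has already provided everything the two-week step endpoint needs, so has not withdrawn from its collection. On the plain reading that patient is not an event, although Table 4 counts the withdrawal. Days 15 to 90 are 76 of the 90 post-discharge days.

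There is a second problem of meaning. In a joint model the treatment coefficient in the hazard part is conditional on whatever is shared with the longitudinal part. If that is the current step level, the coefficient is a direct effect given steps, not the overall effect of being assigned to telemonitoring.

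The stake is the conclusion on burden. A statement about three to four months of monitoring could rest on the first two weeks at home, and on a hazard ratio whose interpretation depends on an unrecorded modelling choice.

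**Working it through.** **1. The plan's own figure.** Section 13.2 claims at least 80% power for Aim 3 with n=332, from a two-sample comparison of proportions. Rates, alpha, sidedness and margin are absent, so the figure can be neither reproduced nor refuted. With 166 per arm and two-sided alpha 0.05 (assumed), 80% power needs 10% v 21.1%, 20% v 33.6%, or 30% v 44.8%. Check for the middle pair: z = (0.136 − 1.96 × 0.0486) / 0.0480 = 0.85, and Φ(0.85) = 0.80. Whatever rates were used, this is an unconditional contrast between arms at some horizon, which is not the planned estimate.

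**2. Inputs for the window.**
- n = 332, randomised 1:1 (section 13.2).
- 20% attrition in accelerometer use by Day 14, both arms together (section 13.2, Aim 1). Device loss is part of the Aim 3 endpoint, so this is the closest figure in the plan.
- Assumed: constant hazard to Day 14, then a fraction f of it to Day 90; hazard ratio 1.5; two-sided alpha 0.05. The plan gives no Aim 3 effect size and no hazard after Day 14.

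**3. Formulas.** Early hazard h = −ln(0.8)/14 = 0.01594 per day. Withdrawn by Day 90 = 1 − 0.8 × exp(−76·f·h). Events = 332 × proportion withdrawn. Power = Φ(√(events/4) × ln 1.5 − 1.96), by Schoenfeld's formula.

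| Horizon | Withdrawn | Events | Power, HR 1.5 | Withdrawals after Day 14 |
|---|---|---|---|---|
| Day 14 | 20.0% | 66 | 38% | – |
| Day 90, f = 0.10 | 29.1% | 97 | 51% | 31% |
| Day 90, f = 0.25 | 40.9% | 136 | 66% | 51% |
| Day 90, f = 0.50 | 56.3% | 187 | 79% | 65% |

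The last column is 1 − 20%/withdrawn; for f = 0.10, 1 − 0.200/0.291 = 31%.

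**4. If burden builds up late.** Suppose the arms are equal at 20% to Day 14 and the hazard ratio is 1.5 afterwards. Day-90 withdrawal is then 29.1% v 33.3% (f = 0.10), 40.9% v 49.2% (f = 0.25) or 56.3% v 67.8% (f = 0.50). An analysis ending at Day 14 shows a hazard ratio of 1.0 in all three.

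**5. Conditioning on steps.** Two links fit the text:
- Current value: hazard = h0(t) · exp(γ·treatment + α·steps at t).
- Shared random intercept: hazard = h0(t) · exp(γ·treatment + α·patient effect).

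Assume α = −0.02 per percentage point of steps, an arm difference growing to 14 points at Day 14, and a random-intercept SD of 20. In a simulation of 200,000 patients, a sub-model hazard ratio of 1.00 corresponds to an unconditional 0.88 to Day 14 under the current-value link, and 1.30 corresponds to 1.13. A hand check at half the final difference agrees: exp(−0.02 × 7) = 0.87, and 1.30 × 0.87 = 1.13. Under the shared random intercept, 1.00 stays 1.00 and 1.30 becomes 1.28. The link therefore decides whether conditioning matters.

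**The case against.** A reader might infer that the plan cuts Aim 3 off at Day 14. The documents do not say so. The outcome of the hazard sub-model is named as the Aim 3 endpoint, which Table 4 collects to the end. Event times in a joint model may run past the last longitudinal measurement, and steps are recorded to Day 90. Aim 1 also has joint models for secondary endpoints, with no window given. What stands against this is that the event is tied to collection of a two-week endpoint, and nothing in section 13.2 extends it. The defect is an unstated horizon whose plain reading is two weeks, not a documented truncation.

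A reader might also infer that the hazard ratio necessarily removes any effect acting through activity. That is not supported either. The only shared element the text suggests is a random patient effect, and under a shared random intercept the distortion in the illustration is small.

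The loss of withdrawals before surgery might be blamed on the joint model. It comes instead from the ITT definition in section 13.2, which admits only randomised patients who had the planned surgery.

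Finally, the size of the gap is uncertain. Carrying the early hazard unchanged to Day 90 would give 76% withdrawn, which no section supports. Section 3.1 expects 332 of 398 evaluable at Day 30, a loss of 66/398 = 16.6%. That may measure something other than accelerometer use, but it gives no sign of steady loss after Day 14. If later withdrawal were close to nil, the two horizons would nearly coincide.

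**Conclusion.** The point holds as a mismatch between a named endpoint and its only analysis. Withdrawal is defined over the whole study. The planned estimate, read plainly, covers about two weeks after discharge and may be conditional on steps. Because neither horizon nor link is fixed, the reported hazard ratio would have no settled meaning, and the plan describes no step that recovers an overall effect from the two sub-models.

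The event counts and power in the table are illustrations. They rest on the plan's 20% by Day 14, an assumed hazard ratio of 1.5 and assumed later hazards. The conditioning figures rest on assumed parameters and matter only under a current-value type of link. The claims that Aim 3 is certainly truncated at Day 14, or certainly conditional on steps, go further than the text allows.

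**What to change.** Keep the joint model for Aim 1, where it serves to handle missing step data, and state its link and censoring day.

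For Aim 3, report a stand-alone proportional hazards (or cumulative-incidence) comparison of time to dropout or device loss, not conditional on steps, censored at Day 90 post-discharge, in the plan's ITT population. State the time origin and, if cumulative incidence is used, the competing events. Counting withdrawals before surgery among patients who never have the operation would need an explicit exception to the ITT definition, because it changes the analysis population. Restate the Aim 3 power for this comparison, with its rates, alpha, sidedness and any margin.

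The cost is SAP wording and one extra model on data already collected. Aim 2 already needs dates of withdrawal from the study through 90 days, as a competing endpoint for readmission.

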Patients will complete patient reported outcomes and objective assessments of functional activity before surgery. Patients will then be randomized to either the remote perioperative telemonitoring care group or surgeon only perioperative care group.

Following surgery and before discharge, patients will complete patient reported outcomes. Patients will complete patient reported outcomes day 7, 14, 30, 60, and 90 post-discharge from hospital. On day 90 post-discharge, patients will participate in a brief open-ended exit surveys.

Patients will be provided a patient packet, which includes a research team contact list, patient calendar, and Activity Monitor Tracking Sheet. The patient calendar will provide key dates for patient assessments, while the Activity Monitor Tracking Sheet will track specific times when the Actigraph is not worn and patient sleeping hours. An informational brochure containing key information about this study will also be given to patient in the enrollment process.

Focus Group - In months 18-30 (Years 2-3) of the project, we will conduct 5 (4 for patients/families, 1 for surgeons/nurses) qualitative focus groups to understand the perioperative telemonitoring experiences from the patients, families, and surgeons/nurses perspectives. Focus groups are a form of focused interview⁶⁷ with the goal of examining an experience that respondents all have had and can speak about. The advantages of focus groups are 1) the group production of data and, 2) data-collection efficiency. Participants are often reassured to hear similar experiences on the part of others, and feel empowered to talk about their own ideas.⁸⁴ The patient focus groups will solicit overall perioperative care experiences, while the open-ended exit surveys will focus specifically on the perioperative telemonitoring acceptability. A total of four focus groups will be conducted with patients/families. Two will include English-speaking

patients, with one focusing on older adults (65 or older), and one on younger adults (65 or younger). Both groups will enroll a total of 6-9 participants with equal representation by cancer type (GI, GU, GYN). The two focus groups for Spanish-speaking patients will follow the same pattern. Equal representation by cancer type will be used for the one surgeon/nurse focus group.

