Focus Group Guides - The semi-structured questions for focus groups are designed to solicit patient/families and surgeon/nurse perspectives on the following: 1) overall perceptions of perioperative care; 2) unmet needs during pre-and postoperative care; 3) greatest challenges before and after surgery; 4) postoperative recovery process at home; 4) use of telemonitoring application for communication (surgeon/nurses); 5) use of telemonitoring dashboard to guide clinical care (surgeon/nurses).

Exit Surveys – This survey contains several open-ended questions that participants in the perioperative telemonitoring arm will complete. The participants will provide information via written comments. The questions are designed to solicit feedback on the following: 1) on-boarding and setup process; 2) use and setup process of accelerometer; 3) value of monitoring PROs and functional activity;; 4) satisfaction with the timing of the telemonitoring (starts before surgery and continues up to 3 months after discharge from hospital); 5) satisfaction with the methods/technology used (mobile application, wristband watch) 6) most useful components of the telemonitoring for helping with postoperative recovery; 7) likes/dislikes of the program; 8) challenges and limitations of telemonitoring; and 9) suggestions on areas for improvement.

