Aim 4 - Qualitative data from exit interviews and focus groups will be analyzed using the conventional content analysis approach.⁷³ Written survey comments will be transferred to, and data from the audio-recorded focus groups will be transcribed and analyzed using HyperRESEARCH™ qualitative software. Transcripts will be imported allowing for the development of analytic categories, data coding, and review of coded data. All data will be read repeatedly to achieve immersion and obtain a sense of the whole. Then, data will be read to derive codes, and sorted into themes based on links and relationship. [name] and [name] will conduct a final validation review of the codes/themes to ensure consistency and clarity across all qualitative data. Data discordantly coded will be discussed for refinement and consensus purposes with the SAC.

The team will use a mixed methods approach to enhance interpretation of study findings. For interpretation of study findings, the exit survey and focus group data will be used to augment quantitative data in Aims 1-3 (perioperative experience with functional recovery, symptoms,

sedentary time, postoperative complications, hospital readmissions, burden of telemonitoring). One approach to qualitative analysis is to use the quantitative outcomes of interest as themes for coding the qualitative data. Therefore, each quantitative outcome of interest will have corresponding qualitative data in the participants and stakeholder's own words. The table below illustrates the connection between quantitative and qualitative data.

Quantitative Outcomes	Connections with Qualitative Data
Functional recovery/sedentary time	Patient/family partner focus groups – overall experience with postop functional recovery/sedentary time
Sleep, symptom severity, symptom interference with daily activities	Patient/family partner focus groups – overall experience with postop symptoms
Postoperative complications (Comprehensive Complications Index – CCI) and related secondary surgical outcomes (hospital readmission).	Surgeon-nurses focus groups Patient/family partner focus groups – overall experience
Early withdrawal (dropout or loss of accelerometer device)	Telemonitoring arm open-ended exit survey

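### The only qualitative source paired with early withdrawal is a Day 90 exit survey, so patients who drop out sooner are not asked why they left

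*Combined protocol and SAP*

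**What the plan says.** - **Timing.** Section 5.1 (Study Procedures): "On day 90 post-discharge, patients will participate in a brief open-ended exit surveys". In Table 4 of section 10.0 the row "Open-Ended Patient Exit Survey" carries a single mark. The table is broken in the text available, but the mark appears to fall at Day 90, which agrees with section 5.1. No other time is given.
- **Who answers.** Section 12.1.3: "This survey contains several open-ended questions that participants in the perioperative telemonitoring arm will complete". Its topics include likes and dislikes and "challenges and limitations of telemonitoring". No listed topic asks why a patient stopped.
- **Use.** Section 13.2 (Aim 4) says that "the exit survey and focus group data will be used to augment quantitative data in Aims 1-3", and burden of telemonitoring is in the list that follows. It undertakes to match each quantitative outcome with qualitative data. In the row for early withdrawal, the only source is "Telemonitoring arm open-ended exit survey".
- **The aim it supports.** Section 1.0, Aim 3: "Hypothesis: Remote perioperative telemonitoring does not excessively burden patients and families". Section 13.2 tests this by proportional hazards regression of time to early withdrawal, by intention to treat.
- **Reasons.** Section 4.2 plans to ask patients who decline enrolment for their reasons, if they are willing. Section 5.3 says only that a participant may choose to stop. No section asks for or records a reason at withdrawal.

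**The concern.** A survey meant to illuminate early withdrawal is scheduled at the end of follow-up, when those who dropped out have already gone. Its respondents are completers, plus patients who lost the device but remained. The patients best placed to say whether the programme was too much for them are not asked.

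This bears on how Aim 3 is read. The hazard comparison shows how many left and when, and it pools dropout with device loss. It does not show cause. Similar withdrawal in the two arms could arise if telemonitoring caused more exits from burden and fewer from illness, and the two offset each other. Section 13.2 itself expects step data to be missing not at random, through adverse events, distress or withdrawn consent, yet no form captures which of these applied. For Aim 4, themes on burden and acceptability would be drawn from a group selected for having stayed.

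**Working it through.** No power or alpha calculation decides this. The schedule does, and the only arithmetic concerns how many patients might be missed.

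**Step 1: can a dropout answer the survey?**
- Dropout before Day 90: the survey falls after the patient has left, and no earlier administration is described. Not covered.
- Device lost, patient stays: still in the study at Day 90. Covered.
- Completer: covered.

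**Step 2: does another planned source give the reason?**

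| Source | Section | What it gives | Gap |
|---|---|---|---|
| Patient/family focus groups | 5.1, 12.1.3, 13.2 | Random draw, not limited to completers; burden is in the general list of uses | Section 5.1 directs them to overall perioperative experience and leaves telemonitoring acceptability to the exit survey. The two telemonitoring topics in the guide are marked for surgeons and nurses |
| Technology-issue log | 5.1 | Technical problems, monitored throughout | Not tied to withdrawal; silent on burden and illness |
| CCI and readmission audit | 12.1.3, 13.2 | Complications, readmissions and their reasons | Shows illness, not whether illness led to withdrawal |
| Staff contact when data are missing | 13.2 | A call to re-engage the patient | Nothing is specified to be recorded |

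Each source helps in part. None is a withdrawal reason.

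**Step 3: how many?** Inputs from section 3.1: 398 enrolled (199 per group), 20% attrition, 332 evaluable (166 per group) at 30 days. From section 13.2, Aim 1: 20% attrition in accelerometer use by Day 14, across both arms.

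Reproducing the plan's figure: 332 × 1.20 = 398.4, which matches 398. Applied forwards, 398 × 0.80 = 318.4, not 332. The loss implied by 398 to 332 is 1 − 332/398 = 16.6%.

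Per arm:
- at 20%: 199 × 0.20 = 39.8, about 40
- at 16.6%: 199 − 166 = 33

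Neither figure counts dropouts by Day 90. The first is device use at Day 14, the second is evaluability at Day 30, and neither is specific to the telemonitoring arm. If a share s of these losses were true dropouts (s is not in the documents), the early losses missed by the survey would be:

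| Assumed s | 33 × s | 39.8 × s |
|---|---|---|
| 0% | 0 | 0 |
| 25% | 8 | 10 |
| 50% | 17 | 20 |
| 100% | 33 | 40 |

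Dropouts between Day 14 or Day 30 and Day 90 would add to these. The documents give no figure for them.

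**The case against.** The strongest reply is that burden is tested elsewhere. A reader might infer from the survey's timing that all the evidence on burden comes from patients who stayed, so that Aim 3 rests on a survivor sample. The documents do not support that. Aim 3 compares time to early withdrawal by intention to treat among randomised patients who had the planned surgery, and there the dropouts are the events. This part of the objection stands in full.

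Second, the Aim 4 table is offered as an illustration, and section 13.2 says in general terms that focus groups also inform burden. This stands in part: focus groups may include a dropout by chance, but the table assigns them no role for withdrawal.

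Third, a count of missed patients cannot be read off the 20% attrition, since someone who stops wearing the device can still complete the survey. This stands; the number is unknown.

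Fourth, it is tempting to conclude that the survey will make the programme look more acceptable than it was. That direction is plausible but not shown. The survey yields coded comments rather than an acceptability rate, and it asks every respondent about dislikes and challenges. The likely loss is in the range of themes.

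Finally, Aim 4 is exploratory, and no primary endpoint, test or sample size depends on this survey. That limits how serious the point is.

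**Conclusion.** The point holds as a gap in the qualitative evidence. As scheduled, the one qualitative source that the Aim 4 table assigns to early withdrawal does not reach patients who drop out before Day 90, and no reason for leaving is recorded. The plan can estimate whether and when withdrawal differs by arm, but can say only indirectly why it happened.

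The conclusion rests on the stated schedule and on the absence of any text providing an earlier survey. Nothing forbids staff from giving one. The size cannot be fixed from the documents: 33 to 40 per arm describes early attrition of any kind, not missed respondents. Severity is minor, and the change is worth making because it is cheap and because reasons not captured at withdrawal are hard to recover later.

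**What to change.** In sections 5.1 and 12.1.3 and in Table 4, schedule the exit survey for Day 90 or early withdrawal, whichever comes first. At withdrawal, existing staff offer the same form on a voluntary basis, with one added item on the main reason for stopping. Because early withdrawal is defined to include device loss, state whether a patient who loses the device but stays in the study answers then or at Day 90.

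In section 13.2 (Aim 4), report withdrawers and completers separately, with the number in each group who were offered the survey and the number who answered. Asking the single reason item in the surgeon-only arm as well would let reasons be compared between arms. That is optional, since the survey is otherwise confined to the telemonitoring arm.

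The cost is a minor IRB amendment and a little staff time. Some withdrawers will decline, so the selection is reduced rather than removed.
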